### **5.3. Screen Failures**

Screen failures are defined as participants who consent to participate in the clinical study but are not subsequently randomized to study intervention. A minimal set of screen failure information is required to ensure transparent reporting of screen failure participants to meet the Consolidated Standards of Reporting Trials (CONSORT) publishing requirements and to respond to queries from regulatory authorities. At a minimum, the following information will be entered into the electronic case report form (eCRF): demography, reason(s) for screen failure, and any study procedure-related SAEs.

Individuals whose laboratory results initially do not meet the criteria for participation in this study may have the test(s) repeated one time within 10 days; if the repeat value is not exclusionary, the participant may be eligible for enrollment and randomization.

## 6. STUDY INTERVENTION

Study intervention is defined as any investigational intervention, marketed products, or placebo intended to be administered to a study participant according to the study protocol.

### 6.1. Study Intervention(s) Administered

Details of dociparstat solution for injection are listed in [Table 2](#).

**Table 2: Dociparstat Details**

Intervention Name	Dociparstat sodium
Type	Drug
Dose Formulation	Solution for injection
Unit Dose Strength(s)	50 mg/mL
Route of Administration	Intravenous infusion (Bolus then continuous IV infusion)
Use	Experimental agent
IMP and NIMP	IMP
Sourcing	Provided centrally by the sponsor
Packaging and Labeling	Provided in 10-mL vials (4 vials/carton). Vials will be supplied to sites in a bulk manner. Each carton will contain 4 vials for individual use and will be labeled in accordance with applicable regulatory requirements
Current/ Former Names	DSTAT, CX-01, ODSH

Normal saline (sodium chloride 0.9%) will be used to dilute dociparstat solution for injection before each infusion. In order to maintain blinding of randomized study intervention, normal saline will also be used as the de facto placebo. Commercially-available product will be purchased and provided locally by the study site (or subsidiary or designee); packaging and labeling will be per local requirements for commercial products.

Dociparstat sodium solution for injection is supplied in 10-mL vials. Vials will be supplied in a bulk manner in a carton containing 4 vials per carton for individual use. Calculate dosing based on participant's screening weight and prepare/dilute the drug product before IV infusion. Dociparstat must be administered via a dedicated infusion line. Do not mix with other IV medications.

Dociparstat is administered as an initial IV bolus dose, immediately followed by a continuous IV infusion 24 hours daily for 7 days (see [Table 3](#)).

**Table 3: Dosing Regimen: Bolus Dose plus Continuous Infusion**

Study Intervention Dosing	
All Participants:	
 
• Dociparstat 4 mg/kg or placebo IV bolus on Day 1, followed by
 
• Dociparstat or placebo by continuous IV infusion for 24 hours daily for 7 days (starting on Day 1 and ending on Day 8 [168 hours])
 

Dociparstat Continuous Infusion Dose by Cohort	
Phase 2, Cohort 1	
 
• 0.25 mg/kg/hr
 

Phase 2, Cohort 2	
 
• 0.325 mg/kg/hr (dose to be confirmed after DMC review of data from Cohort 1)
 

Phase 2, Cohort 3	
 
• 0.25 or 0.325 mg/kg/hr (dose to be confirmed after DMC review of data from prior cohorts)
 

Phase 3	
 
• 0.25 or 0.325 mg/kg/hr (dose will be the same as used in Cohort 3)
 

## 6.2. Preparation, Handling, Storage, and Accountability

### 6.2.1. Dose Preparation

Preparation of randomized study intervention (i.e., dociparstat or placebo) will be performed by an unblinded pharmacist within the investigational pharmacy. The pharmacist will prepare study intervention to the appropriate dose based on the individual participant's body weight. Normal saline will be used to dilute the IV bolus dose and continuous maintenance infusion of dociparstat treatment. The dociparstat IV bolus dose will be diluted to a total infusion volume of 30 mL. The 24-hour continuous infusion will have the appropriate volume of dociparstat added to approximately 250 mL or 500 mL of 0.9% normal saline.

The placebo IV bolus dose will be a total infusion volume of 30 mL of 0.9% normal saline only. Placebo for the continuous infusion will be 250 mL or 500 mL of 0.9% normal saline only.

Sites will follow their own labeling procedures to identify prepared study intervention (i.e., dociparstat or placebo) for each participant in a blinded manner.

### 6.2.2. Handling, Storage, and Accountability

A sufficient quantity of dociparstat vials will be supplied to the investigator (or qualified designee) at each study center. Vials will be shipped in a carton containing 4 vials per carton. The vials will be supplied in a bulk manner to allow individual assignment of vials to participants. Once received at the study center, vials of dociparstat should be stored in accordance with the labeled storage conditions, in a securely locked area, with access limited to the unblinded pharmacist and authorized site staff.

Dociparstat should be stored at controlled room temperature (i.e., 15°C to 25°C [59°F to 77°F]), with excursions permitted to 30°C (86°F); protect from freezing.

The investigator or qualified designee (e.g., unblinded pharmacist) must confirm appropriate temperature conditions have been maintained during transit for all study intervention received and must report and resolve any discrepancies before use of the study intervention.

The investigator's qualified designee (e.g., unblinded pharmacist) is responsible for ensuring adequate accountability of all used and unused study intervention. This includes acknowledgment of receipt of the shipment(s) of study intervention (date, quantity, and condition), participant dispensing records, and returned or destroyed vials. Dispensing records will document the dispensing of the vials to individual participants (including vial number, date dispensed, and participant identifier number), the initials of the person(s) dispensing the study interventions, and the return and/or disposal of the study intervention. All study intervention records must be maintained at the site and copies must be submitted to Chimerix at the end of the study.

After verification of the study intervention records by the unblinded study monitor, all remaining study intervention supplies should be destroyed according to directions provided by Chimerix (or its designee) and/or any applicable site-specific standard operating procedures. If necessary, unused study intervention supplies may also be returned to the appropriate depot with prior approval from Chimerix (or its designee). If study intervention is destroyed on site, the investigator must maintain accurate records for all study intervention destroyed. Records must show the identification and quantity of each unit destroyed, the method of destruction, and person who disposed of the drug.

Only participants randomized in the study may receive study intervention and only authorized site staff may prepare, supply, or administer study intervention. It is recommended that preparation of each dose of study intervention be confirmed by a second unblinded pharmacist.

### **6.3. Dose Modification**

Dosing will be calculated on the basis of each participant's screening weight.

Criteria for interruption (including resuming dosing at a reduced dose) and discontinuation of study intervention are provided in Section 7.

### **6.4. Measures to Minimize Bias: Randomization and Blinding**

A randomized, double-blind, placebo-controlled study design was selected as the most robust design to minimize potential bias.

Participants who meet all applicable eligibility criteria will be centrally randomized to one of 2 study intervention groups (dociparstat or placebo) using an automated interactive response technology (IRT) system and a computer-generated randomization code provided by the sponsor or designee. Randomization of participants in Cohort 3 and in Phase 3 will be stratified based upon NIAID score (3 or 4) and age (<60 years vs  $\geq$ 60 years). Randomization of participants in Phase 3 will additionally be stratified by baseline BMI ( $<34 \text{ kg/m}^2$  or  $\geq 34 \text{ kg/m}^2$ ).

Once a randomization number has been assigned, it will not be re-assigned to any other participant in the study. The IRT system will also be used to track study intervention dispensing.

Investigators and participants will be blinded to each participant's assigned study intervention throughout the course of the study. In order to maintain this blind, an otherwise uninvolved third

party (an unblinded study pharmacist) will be responsible for the preparation and dispensation of blinded study interventions (i.e., dociparstat and placebo) and will ensure that there are no differences in appearance or time taken to dispense study intervention following randomization. In addition, the bolus syringe and the IV bags will be masked to obscure any visual differences in color between dociparstat and placebo.

In the event of a regulatory inspection or quality assurance audit, the auditor(s) will be allowed access to unblinded study intervention records at the site(s) to verify that randomization and dispensing have been done accurately. Additional roles and responsibilities that require unblinding of specified sponsor (and/or designated contract research organization) personnel not directly involved in the conduct of the study include supply chain, regulatory reporting of expedited safety reports, and DMC reviewers.

Normal saline (sodium chloride 0.9%) will be used as the study intervention placebo for both the loading doses and the continuous infusions. Placebo-controlled studies are the gold standard for clinical trials, as they reduce bias in care and conduct during the study. Though the efficacy endpoints are objective, safety assessments are less biased when treatment allocation is masked.

Modest effects of dociparstat on aPTT have been observed in previous studies. Although the mean aPTT values during the continuous infusion were nominally higher for dociparstat 0.25 mg/kg than control, the individual participant values were variable and had considerable overlap between groups; therefore, individual aPTT measurements are not expected to unblind the participant's treatment assignment. In the current study, potential unblinding will be mitigated by obtaining initial aPTT measurements no sooner than 8 hours after the bolus infusion (after the time of peak effect) and by instructions to obtain blood for aPTT measurements from a location that is separate from the dociparstat infusion. Specifically, blood should be obtained via separate venipuncture and/or a catheter separate from the one used to administer study intervention. If the specimen is drawn from a heparinized line, first draw 5 mL of blood from the line for discard before drawing the aPTT sample.

The IRT will be used for blind-breaking instructions. In case of an emergency, the investigator has the sole responsibility for determining if unblinding of a participant's intervention assignment is warranted. Participant safety must always be the first consideration in making such a determination. If the investigator decides that unblinding is warranted, the investigator should make every effort to contact the sponsor prior to unblinding a participant's intervention assignment unless this could delay emergency treatment. If a participant's intervention assignment is unblinded, the sponsor must be notified within 24 hours after breaking the blind. The date and reason that the blind was broken must be recorded in the source documentation and eCRF, as applicable.

## **6.5. Study Intervention Compliance**

Participants will receive study intervention directly from the investigator or qualified designee, under medical supervision. The date and start/stop times of each dose of study intervention administered will be recorded in the source documents and in the eCRF.

Study participant identification will be confirmed at the time of dosing by a member of the site staff other than the person administering the study intervention.

## 6.6. Concomitant Therapy

Information about the participant's concomitant medications/therapies will be collected in the eCRF as specified below.

Collection time periods:

- Prior medications: All medications taken from 14 days prior to the time of signing ICF through time of randomization.
- Concomitant medications: All medications and transfusions from the time of first dose of study intervention on Day 1 through Day 28.

Information to collect:

- Names (nonproprietary names are preferred) for all prescription medications.
- Reason for use (indication).
- Start and end dates of administration.
- Dosage information, including dose, units, route, and frequency.

Contact the medical monitor (or designee) if there are any questions regarding concomitant or prior therapy.

### 6.6.1. Prohibited Therapies

Refer to the exclusion criteria (see Section 5.2) for medications prohibited prior to randomization (and the associated time period) in the study.

The following medications are prohibited through Day 28 (unless otherwise specified):

- Warfarin or direct oral anticoagulants (e.g., rivaroxaban, dabigatran, apixaban, edoxaban).
- Aspirin and any other antiplatelet agents (e.g., clopidogrel, prasugrel, ticagrelor) are prohibited from the time of randomization throughout the duration of the study intervention infusion period.
- Thrombolytic agents.
- Systemic (nonsteroid) immunomodulators or immunosuppressant medications, including but not limited to TNF inhibitors, anti-interleukin-1 agents, and JAK inhibitors.
- Investigational (non-approved) therapy for the treatment of COVID-19, including (but not limited to) the following: favipiravir, tocilizumab or other agents that interfere with IL-6 release/function, or other anti-inflammatory approaches to COVID-19 treatment.

As there is no standard of care or approved treatment options for COVID-19, it is not possible to predict all medications that may be considered during the course of treatment.

Contact the medical monitor for prior approval and to discuss any questions on the use of concomitant therapies for the treatment of COVID-19 and associated sequelae not specified in

the protocol or pharmacy manual. To ensure interpretability of the data and participant safety, administration of concomitant therapies outside of protocol guidelines and without prior approval by the medical monitor will be considered a protocol deviation; however, it is recognized that use of concomitant therapies is always at the investigator's discretion with the health and safety of the study participant as the priority.

#### **6.6.2. Permitted Therapies**

The following medications are permitted during the study:

- Medications for acute (e.g., pain, bacterial infection) or chronic (e.g., hypertension, diabetes) medical conditions, unless otherwise prohibited.
- Prophylaxis for venous thromboembolism using SC unfractionated heparin or enoxaparin with appropriate monitoring of coagulation status. See [Appendix 8](#) for guidelines.
- Remdesivir, per available data sheets/guidance on dosing and toxicity management.
- Convalescent plasma.

For participant's whose condition declines to a 2 on the NIAID ordinal scale (i.e., requires invasive mechanical ventilation or extracorporeal membrane oxygenation), otherwise prohibited treatments may be initiated at the investigator's discretion. In this situation, please contact the medical monitor since discontinuation of study intervention may be warranted if use of an otherwise prohibited treatment (e.g., therapeutic anticoagulant doses) could affect the participant's safety if study intervention were to be continued.

#### **6.7. Intervention After the End of the Study**

Dociparstat is not intended for continued maintenance treatment; therefore, the study intervention will not be provided beyond the protocol-specified treatment period.

After the end of the treatment period, the participants' ongoing medical care and treatment in the event of a recurrence will be the responsibility of the participants' physician(s).

## 7. DISCONTINUATION OF STUDY INTERVENTION AND PARTICIPANT DISCONTINUATION/WITHDRAWAL

All reasons for dose interruption, discontinuation, and study withdrawal must be entered into the eCRF.

### 7.1. Interruption of Study Intervention

Infusion of study intervention (i.e., dociparstat or placebo) will be interrupted in the following situations:

**aPTT:** If aPTT is >50 seconds, repeat testing as soon as practicable. If aPTT is confirmed >50 seconds (or when retest and confirmation cannot occur within the same day), reduce the dose of enoxaparin or unfractionated heparin (as applicable). If aPTT remains elevated upon repeat testing, then interrupt the study intervention infusion. [Note: ensure aPTT samples were not obtained from the same line as the study intervention infusion (e.g., collect samples via peripheral venipuncture).]

- Participants in cohorts with dociparstat dosed at 0.25 mg/kg/hr: study intervention dosing will not be resumed if interruption criteria are met.
- Participants in cohorts with dociparstat dosed at 0.325 mg/kg/hr: To minimize time that the participant is off therapy, perform repeat testing for aPTT approximately 2 to 6 hours after interruption (as practicable). When aPTT is <40 seconds, the infusion may be resumed at a reduced dose of 0.25 mg/kg/hr.

**Renal function:** If the calculated creatinine clearance drops below 30 mL/min or eGFR drops below 30 mL/min/1.73 m^2 prior to or during dosing with study intervention, the infusion will be held until the creatinine clearance or eGFR rises to  $\geq 30$ .

**Thrombocytopenia:** If a participant experiences a decrease in platelet count by  $\geq 50\%$  from baseline value, or has an absolute platelet count of  $<50,000/\text{mm}^3$  they are to be evaluated for possible HIT, per the algorithm in [Appendix 6](#).

Consistent with the mechanism of dociparstat, no evidence of HIT has been identified in clinical studies. However, considering the risk of HIT associated with potential concomitant medications used for venous thromboembolism (VTE) prophylaxis during study participation, it is recommended that investigators evaluate participants for HIT if they meet platelet criteria described above, starting with assessment of the 4Ts score to determine pretest probability, and proceeding with testing per the algorithm for participants who score  $\geq 4$  (considered intermediate or high pretest risk of HIT).

For participants with a 4Ts score  $\geq 4$  who are receiving concomitant VTE prophylaxis permitted per protocol, discontinue heparin or enoxaparin until test results rule out HIT. For those participants with a 4Ts score  $\geq 4$  who are not receiving VTE prophylaxis permitted per protocol, study intervention is to be discontinued, and may only be resumed if test results rule out HIT, and the 7-day treatment period has not ended.

**ECG/QTc:** Heparin is not associated with QT prolongation and no cardiac safety signal has been identified to date in preclinical and clinical dociparstat studies. However, considering the risk of QT prolongation associated with potential concomitant medications (e.g., hydroxychloroquine),

it is recommended that the investigator monitor participants in accordance with the American College of Cardiology (or equivalent) guidelines ([Simpson 2020](#)).

If QTc increases by >60 msec or absolute QTc is >500 msec (or >530-550 msec if QRS >120 msec), discontinue and/or reduce the dose of potentially causative medications (e.g., azithromycin and hydroxychloroquine; see [Appendix 7](#)). Repeat ECG daily. If there is no reduction in QTc after modifications to dosing of other medications (e.g., azithromycin and hydroxychloroquine), discontinue study intervention.

## 7.2. Discontinuation of Study Intervention

In some instances, it may be necessary for a participant to permanently discontinue study intervention before completing the protocol-specified treatment period. Reasons for permanent discontinuation of study intervention may include the following:

- Criteria for restarting study intervention after interruption were not met.
- ALT  $\geq 3$ x ULN (and  $>2$ x baseline value) plus bilirubin  $\geq 2$ x ULN.
- Thrombocytopenia defined as a platelet count of  $<30,000/\text{mm}^3$ .
- Hemorrhagic AE of Grade 3 or higher (graded according to the National Cancer Institute-Common Terminology Criteria for Adverse Events [NCI-CTCAE]).
- Other treatment-related AE of unacceptable severity.
- Condition has improved and participant is eligible for hospital discharge.
- Participant requests to discontinue study intervention.
- Investigator initiates treatment with a therapeutic anticoagulant dose, a thrombolytic agent, or otherwise prohibited therapy that may affect the participant's safety if study intervention were to be continued.
- Investigator determines discontinuation is in the best interests of the participant for safety, behavioral, compliance, or administrative reasons.

Participants who discontinue study intervention early will complete the early discontinuation assessments (refer to the Schedule of Assessments) and will continue to be followed-up through Day 28.

Note: For participants who are discharged from the hospital prior to Day 8, the next visit will be Day 14.

## 7.3. Participant Withdrawal from the Study

It is expected that **all participants** randomized in the study, regardless of completion or discontinuation of study intervention, **will remain in the study for follow up through Day 28**.

- Before withdrawing a participant from the study, clarify and document the specific expectations of the participant's request for withdrawal. The following withdrawal scenarios may apply:
  - Discontinuation of study intervention, but completes remaining study assessments, and agrees to collection of relevant follow-up information (i.e., remains in the study; this is the default scenario).
  - Discontinuation of study intervention and/or refuses further study-specific assessments, but agrees to collection of relevant follow-up information (i.e., remains in the study).
  - Completion or discontinuation of study intervention and/or refuses further assessments, AND withdraws consent for any further study communication or follow-up from the study center (i.e., withdraws from the study); the investigator must document this in the site study records.
- A participant may withdraw from the study at any time at his/her own request, or may be withdrawn at any time at the discretion of the investigator for safety, behavioral, compliance, or administrative reasons.
- At the time of withdrawing from the study, if possible, an early withdrawal visit will be conducted. See the Schedule of Assessments for data to be collected at the time of study withdrawal and follow-up and for any further evaluations that need to be completed.
- If the participant withdraws consent for disclosure of future information, the sponsor may retain and continue to use any data collected before such a withdrawal of consent.
- If a participant withdraws from the study, he/she may request destruction of any samples taken and not tested; the investigator must document this in the site study records.

Discontinuation of specific sites or of the study as a whole are discussed in [Appendix 1](#).

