### 9.4.1. Primary Endpoint

Phase 3: The primary analysis will utilize the ITT analysis set and a Cochran-Mantel-Haenszel test stratified by each of the actual stratification factors. Participants will be counted as failures once they go on a ventilator or die. Number and percentage of failures will be presented for each treatment arm. Cochran-Mantel-Haenszel p-values, estimated common odds ratios, estimated common risk differences, and corresponding approximate two-sided 95% CIs will be presented. The Breslow-Day test will be used to test the homogeneity of the odds ratios across strata. Although missing data are expected to be limited, any such cases will be imputed as failure. A supportive analysis using multiple imputation will be done in order to assess the sensitivity of the inference to the approach to missing data.

Phase 2: A similar methodology will be used; however, multiple imputation will not be done.

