Unknown/Not Answered	xx (xx.x)	xx (xx.x)	xx (xx.x)	xx (xx.x)
Death (during treatment period)	xx (xx.x)	xx (xx.x)	xx (xx.x)	xx (xx.x)

N = Number of subjects in a specific group; n = Number of subjects with data available; Percentages are based on N;

Page X of Y

(Note for programmer: Death (during treatment period) to be derived in case death date = date of last treatment start date or stop date)

Table 6: Study disposition - Randomized Subjects

Study Disposition	DSTAT 0.25 N=xxx	Cohort 1 PBO N=xxx	DSTAT 0.325 N=xxx	Cohort 2 PBO N=xxx
Primary reason for early termination				
Randomized subjects, n (%)	xx (xx.x)	xx (xx.x)	xx (xx.x)	xx (xx.x)
Randomized not treated subjects, n (%)	xx (xx.x)	xx (xx.x)	xx (xx.x)	xx (xx.x)
Treated subjects, n (%)	xx (xx.x)	xx (xx.x)	xx (xx.x)	xx (xx.x)
Completed study, n (%)	xx (xx.x)	xx (xx.x)	xx (xx.x)	xx (xx.x)
Ongoing, n (%)	xx (xx.x)	xx (xx.x)	xx (xx.x)	xx (xx.x)
Discontinued study	xx (xx.x)	xx (xx.x)	xx (xx.x)	xx (xx.x)
Primary reason for study discontinuation, n (%)				
Patient withdrawal of consent	xx (xx.x)	xx (xx.x)	xx (xx.x)	xx (xx.x)
Adverse Event	xx (xx.x)	xx (xx.x)	xx (xx.x)	xx (xx.x)
Use of a prohibited therapy	xx (xx.x)	xx (xx.x)	xx (xx.x)	xx (xx.x)
Non-compliance	xx (xx.x)	xx (xx.x)	xx (xx.x)	xx (xx.x)
Lost to follow-up	xx (xx.x)	xx (xx.x)	xx (xx.x)	xx (xx.x)
Investigator decision	xx (xx.x)	xx (xx.x)	xx (xx.x)	xx (xx.x)
Sponsor decision	xx (xx.x)	xx (xx.x)	xx (xx.x)	xx (xx.x)
Other	xx (xx.x)	xx (xx.x)	xx (xx.x)	xx (xx.x)
Unknown/Not Answered	xx (xx.x)	xx (xx.x)	xx (xx.x)	xx (xx.x)
Death, n (%)	xx (xx.x)	xx (xx.x)	xx (xx.x)	xx (xx.x)

N = Number of randomized subjects in a specific group; n = Number of subjects with data available; Percentages are based on N;

Page X of Y

Table 7: Proportion of subjects who go on invasive mechanical ventilation or ECMO - Safety Set

	DSTAT 0.25 N=xxx	Cohort 1 PBO N=xxx	DSTAT 0.325 N=xxx	Cohort 2 PBO N=xxx
Number of subjects with any invasive mechanical ventilation, ECMO or early study discontinuation, n (%) (a)	xx (xx.x)	xx (xx.x)	xx (xx.x)	xx (xx.x)
Any invasive mechanical ventilation	xx (xx.x)	xx (xx.x)	xx (xx.x)	xx (xx.x)
Early study discontinuation < Day 25	xx (xx.x)	xx (xx.x)	xx (xx.x)	xx (xx.x)
Kaplan-Meier estimates (b)				
Number of censored subjects, n (%) (b)	xx (xx.x)	xx (xx.x)	xx (xx.x)	xx (xx.x)
Time to first invasive mechanical ventilation or ECMO (days) (b)				
25% Quartile (95% CI)	x.x (x.xx,x.xx)	x.x (x.xx,x.xx)	x.x (x.xx,x.xx)	x.x (x.xx,x.xx)

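### Section 7.3 lets the investigator end a participant's study follow-up on the same grounds that 7.2 uses only for stopping treatment, and 9.4.1 would count the lost Day 28 outcome as a failure

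*Protocol*

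**What the plan says.** Protocol 7.3 opens with the expectation that all randomized participants, "regardless of completion or discontinuation of study intervention", "will remain in the study for follow up through Day 28". It then gives three withdrawal scenarios. In the first two the participant remains in the study. Only the third, in which the participant withdraws consent for further contact and follow-up, is labelled as leaving the study. Section 7.4 adds loss to follow-up.

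A later bullet in 7.3 lets participants leave at their own request and adds that a participant "may be withdrawn at any time at the discretion of the investigator for safety, behavioral, compliance, or administrative reasons". This bullet concerns the study, not the treatment.

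Protocol 7.2 uses the same grounds among its reasons for stopping treatment: "Investigator determines discontinuation is in the best interests of the participant for safety, behavioral, compliance, or administrative reasons". Participants who stop treatment early "will continue to be followed-up through Day 28".

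For the primary endpoint, Protocol 9.4.1 says of missing outcomes that "any such cases will be imputed as failure". A multiple-imputation analysis is planned as supportive for Phase 3 and is not done for Phase 2.

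The SAP covers the post-Cohort 1/2 lock only. Its Table 18 counts study discontinuation before Day 25 as an event in the proportion rows, while the Kaplan-Meier rows censor the same people. Its Table 6 lists reasons for leaving the study that include adverse event, "Use of a prohibited therapy", non-compliance and investigator decision.

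**The concern.** The same reason, for example a safety concern, can lead a site to two different actions. Under 7.2 the infusion stops and the outcome is still collected. Under the bullet in 7.3 the participant leaves the study. No text says which applies when the participant has not withdrawn consent.

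The difference matters because of the failure rule. A participant who is alive and unventilated, and whom the investigator removes from the study, may have no Day 28 status. That person is then scored with those who died or were intubated.

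Some of the grounds could differ by arm. Protocol 2.3.1 names aPTT prolongation with possible bleeding, and hepatic enzyme increases, as risks of particular interest. Missing outcomes could therefore be related to treatment. They are also avoidable: ventilation and vital status can be obtained without study procedures, and the second scenario in 7.3 already allows for this.

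**Working it through.** **Inputs.** Failure rates of 20% (placebo) and 9% (dociparstat), two-sided alpha 0.05 and power above 80% come from Protocol 9.2. The arm sizes of 150 and 300 come from 4.1. The non-binding futility look after 225 participants, with bound 0.919, comes from 9.5. Section 9.2 states no dropout allowance. No withdrawal rate is given anywhere, so *w* below is an assumption shown over a range.

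**Reproducing the plan's figure.** This uses a two-proportion z-test with pooled null variance, unstratified and without the futility look:

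- Pooled rate = (150 × 0.20 + 300 × 0.09)/450 = 0.1267
- Null SE = √[0.1267 × 0.8733 × (1/150 + 1/300)] = 0.0333
- Alternative SE = √(0.20 × 0.80/150 + 0.09 × 0.91/300) = 0.0366
- Power = Φ[(0.11 − 1.96 × 0.0333)/0.0366] = 0.890

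With unpooled variance throughout, power is 0.852. To add the futility rule, take δ = 0.11/0.0366 = 3.005 and read 0.919 as a Z value at half the information. Power is then P(Z₁ > 0.919 and Z₂ > 1.96), with means δ√0.5 and δ and correlation √0.5, which gives 0.804. All three exceed 80%, so the stated power is reproduced.

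**Adding withdrawals scored as failure.** Let *w* be the share of otherwise event-free participants who are withdrawn with Day 28 status missing. The observed failure rate is p + (1 − p)*w*. On dociparstat each 1% adds 0.91 points; for example, 0.09 + 0.91 × 0.02 = 0.1082.

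| *w* dociparstat / placebo | Failure, placebo vs dociparstat | Difference (points) | Power, no futility look | Power, futility rule followed |
|---|---|---|---|---|
| 0 / 0 | 20.0% vs 9.0% | 11.0 | 0.890 | 0.804 |
| 1% / 0 | 20.0% vs 9.9% | 10.1 | 0.824 | 0.726 |
| 2% / 0 | 20.0% vs 10.8% | 9.2 | 0.741 | 0.637 |
| 3% / 0 | 20.0% vs 11.7% | 8.3 | 0.642 | 0.540 |
| 5% / 0 | 20.0% vs 13.6% | 6.5 | 0.429 | 0.349 |
| 2% / 2% | 21.6% vs 10.8% | 10.8 | 0.847 | 0.756 |
| 5% / 5% | 24.0% vs 13.6% | 10.5 | 0.779 | 0.686 |
| 5% / 2% | 21.6% vs 13.6% | 8.1 | 0.584 | 0.489 |

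The last column uses the unpooled variance, so part of its gap from the column before reflects the variance choice and not the futility rule.

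With withdrawals on dociparstat only, power without the futility look drops below 80% at *w* of about 1.3%. That is about 4 of the 300 × 0.91 = 273 event-free dociparstat participants expected. Erasing the 11-point difference would take 0.11/0.91 = 12.1%, or 33 of the 273.

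**The case against.** Several points on the other side stand.

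- The Day 28 statement in 7.3 is worded as an expectation. A reader might infer a flat contradiction of an absolute rule, but the text does not go that far. It is an expectation followed by an unqualified discretion that points the other way.
- A reader might infer that drug side effects become primary-endpoint failures. They do not by themselves. Under 7.2, Grade 3 or higher hemorrhage, failure to meet restart criteria (which covers aPTT) and starting a therapeutic anticoagulant or other prohibited therapy are reasons to stop treatment, with follow-up to Day 28. A failure needs a further discretionary act of study withdrawal, in someone not already ventilated or dead, that leaves the outcome missing. Section 8.4.3 also asks that serious, special-interest, treatment-related and treatment-stopping events be followed to resolution or stabilization.
- An excess of withdrawals on dociparstat is plausible but not shown. In the COPD study described in 4.3, an ALT effect was seen in 37% of dociparstat and 11% of placebo recipients. However, minor or moderate bleeding was rare and SAEs occurred in 17 versus 14 participants. The AML study showed no serious-bleeding imbalance at 0.25 mg/kg/hr.
- The SAP tables cannot show how Phase 3 will be handled. They cover Cohorts 1 and 2, whose data are descriptive under 9.4. For Phase 3 the point rests on 7.3 and 9.4.1.
- Phase 3 has the supportive multiple-imputation analysis.

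What these points do not remove is the bullet itself. Nothing in 7.2 or 7.3 restricts it to participants who have withdrawn consent. Multiple imputation leaves the primary result unchanged and cannot recover outcomes that were never collected.

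**Conclusion.** The point holds as an avoidable source of possibly treatment-related missing outcomes, created by one bullet that does not fit the rest of 7.3 or 7.2. It should be changed.

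Its size depends on rates the documents do not give. Without the futility look, power falls from 0.89 to 0.82, 0.74 or 0.43 when 1%, 2% or 5% of event-free dociparstat participants, and no placebo participants, are withdrawn. It falls to 0.85 or 0.78 with equal withdrawal of 2% or 5%. The dociparstat-only rows are the unfavourable end of the range. All rows assume that each withdrawal leaves Day 28 status missing.

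A reader might take the bias to threaten a false claim of benefit. If the excess is on dociparstat, it runs against the drug: the harm is lost power and an endpoint that mixes clinical events with administrative loss. Nor do these results show that the stated power is wrong; it is reproduced at the planning rates.

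**What to change.** Reconcile 7.3 with 7.2. State in 7.3 that investigator-initiated withdrawal on these four grounds ends study intervention and, if needed, study-specific procedures. State also that vital status and ventilation status continue to be collected through Day 28, by chart or telephone, with three exceptions: the participant or representative withdraws consent for follow-up, the participant is lost to follow-up under 7.4, or the site or study is closed.

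Keep the reasons in SAP Table 6. Deleting them might look like the natural companion change, but it would move any such withdrawal into the other category and hide it.

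The cost is a short protocol clarification and a little more follow-up work at sites. The sample size, the criteria for stopping treatment and the participant's right to withdraw are unchanged. With *w* = 0, power stays at 0.890, or 0.804 with the futility rule followed.
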